simultaneous image acquisition with excellent PET sensitivity (3x higher sensitivity than conventional PET scanners on campus) and colocation of MR and PET images. This system will allow us to assess dynamic glucose uptake in a unique cohort of formerly premature young adults followed here at UW. Correlation of PET imaging in this cohort with MRI acquired measures of cardiac function will allow for assessment of metabolic efficiency. Furthermore, given that both our animal data and previous exercise studies show the most significant changes during hypoxia exposure, we will use hypoxic scanning conditions to accentuate differences in substrate utilization in formerly preterm young adults. Cardiac glucose utilization has previously been shown to acutely increase as much as 70% during hypoxia exposure in humans, despite unchanged glucose uptake in other tissues,²² and thus will serve as an appropriate myocardial stressor. We anticipate identifying an enhanced 'glycolytic reserve' in formerly preterm young adults, thus helping to explain their improved tolerance to hypoxic conditions.

Specific Aims/Objectives

Specific Aim 1: Identify alterations in cardiac metabolic substrate utilization and metabolic efficiency in formerly premature young adult human subjects using a rest (normoxia)-stress (hypoxia) protocol.

- SA1a: To demonstrate enhanced cardiac glucose uptake in adults born premature utilizing 18F-fluorodeoxyglucose (FDG) PET-MRI.
- SA1b: To correlate dynamic glucose uptake by positron emission tomography (PET) imaging with RV structural and functional measurements by cardiac MRI, providing a measure of metabolic efficiency.
- SA1c: Assess whether blood biomarkers (i.e. proteins) of heart failure and pulmonary vascular disease differ between adults born preterm and term.

Rationale: Formerly preterm young adults exhibit improved tolerance to hypoxic exercise, a phenomenon that exemplifies the relevance of our animal studies. Since increased glucose utilization has previously been demonstrated in RVs from patients with PH secondary to congenital heart disease, considered a protective early postnatal priming event, we propose that such an increase in glucose uptake will also be present in formerly preterm young adults, thus allowing for a more adaptive RV phenotype upon hypoxic RV stress.

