Heart rate, oxygen saturation, and blood pressure will be monitored periodically during MRI scanning, and approximately every 10 minutes during PET scanning. Oxygen saturations and heart rate will be monitored throughout the study, and hypoxic challenge terminated early (transitioned to normoxia) in the event the subject experiences sustained oxygen saturations <75% or heart rate sustained above 100 beats per minute associated with symptoms of dyspnea, chest pain, or palpitations. Decisions to terminate the study altogether will be made by the PI ([name]) or other qualified research personnel (MD or RN). A qualified research team member will be present for scans. When an MD is not physically present in the imaging suite, a physician will be available by phone/pager for all studies and able to physically respond if needed. Given that the [name] lab has previously conducted exercise testing in similar degrees of hypoxia in this population, we anticipate this degree of hypoxia during rest will be well tolerated.¹⁹ Serum glucose and lactate levels, as an indicator of increase in anaerobic metabolism and lactic acidosis, and thereby suggesting decreased glucose oxidation, as well as serum for FDG activity level, will be obtained approximately every 10 minutes during PET scanning.²²

All PET imaging data will be corrected for scatter and measured photon attenuation. PET data will be collected in list mode enabling flexible retrospective reconstruction of images. Images will be reconstructed in six 10-minute images and exported for offline analysis with Mirada (Mirada Medical, Oxford, UK). Regions of interest (ROIs) will be manually drawn over the RV and left ventricle (LV) (apical, mid-ventricular, and basal short axis slices) and standardized uptake value (SUV) determined to quantify ^{18}F -FDG uptake. Endpoints assessed will include the mean and

Title: Cardiac function and metabolism in young adults born premature

PI: [name]

Protocol version date: V7 04/23/2019

maximal SUV within RV and LV, and ratio of RV:LV ^{18}F -FDG uptake (previously correlated with RV function²⁴) for each of the six PET images.

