EKG and respiratory gated cardiac MRI will be performed simultaneously with PET imaging, allowing for colocation of cardiac structures with ^{18}F -FDG uptake. RV and LV function will be evaluated using an EKG-gated, balanced steady-state free precession (SSFP) technique. Axial SSFP images will be acquired through the entire heart to minimize inter-observer and intra-observer variability.²⁵ Conventional short axis, 2-chamber, 3-chamber, and 4-chamber views will also be acquired, in accordance with standard clinical cardiac exam. Parameters for the SSFP images will be individually adapted to each participant's individual anatomy while optimizing image quality. In addition to a standard clinical cardiac exam, research sequences will include but not limited to: PC VIPR, SMART T1 map, 3D KAT-Arc Cine to provide detailed assessments of flow, T1, and cardiac functional morphology that are not routinely acquired in conventional clinical exams.

All PET/MRI hardware is FDA approved. Most software is FDA approved and used routinely in clinical care. Investigational MRI software developed by UW or GE Healthcare will be used for this research. The novel software will continue to meet the criteria for classification as Non-Significant Risk by FDA guidelines outlined in 21 CFR 812.3. Specifically:

1. It is not intended as an implant and presents a potential for serious risk to the health, safety, or welfare of a subject;
2. It is not purported or represented to be for use supporting or sustaining human life and presents a potential for serious risk to the health, safety or welfare of a subject;
3. It is not for a use of substantial importance in diagnosing, curing, mitigating, or treating disease, or otherwise preventing impairment of human health and presents a potential for serious risk to the health, safety or welfare of a subject; or
4. It does not otherwise present a potential for serious risk to the health, safety, or welfare of a subject.

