Image analysis will be offline. Using MATLAB (The Mathworks, Natick, MA) custom software or similar for quantitative modeling and analysis, RV and LV wall thickness and mass will be manually determined offline. RV end diastolic and end systolic volumes will be determined by semi-automated detection with fine manual adjustment of cardiac borders, allowing for calculation of RV ejection fraction and stroke volume. Finally, the Tei Index, a measure RV function previously correlated with glucose uptake in patients with PH, will be calculated as the isovolumetric contraction time plus isovolumetric relaxation time divided by the total ejection time.²⁶ Cardiac metabolic efficiency will be assessed as both a ratio of maximal SUV uptake to cardiac output and of maximal SUV uptake to Tei index.

Pulmonary function testing: Subjects will undergo non-invasive pulmonary function testing including spirometry, plethysmography (for lung volumes) and diffusion capacity, according to standard clinical testing. All procedures are performed according to standard clinical practice and all devices are non-investigational.

EKG: Subjects will undergo non-invasive EKG. Procedure is performed according to standard clinical practice and all devices are non-investigational. EKG will be reviewed by study personnel prior to imaging. Any subject not in a sinus rhythm will be excluded from imaging (sinus arrhythmia allowed), as hypoxia could exacerbate arrhythmias. Such findings will be discussed with the study participant immediately.

Title: Cardiac function and metabolism in young adults born premature

PI: [name]

Protocol version date: V7 04/23/2019

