There is a risk of breach of confidentiality. In order to protect against this risk, all data will be stored on a secure, password protected network. All data will be identified using unique identification numbers, not names, date of birth, or other identifiable information. In files where identifiable information is linked to the unique ID number, only staff members who specifically use this information for contacting participants, etc. will have access. All PET/MR scans performed for research purposes only will be given a unique study number that cannot be linked to the patients' hospital medical records in any way. PET/MR research images will be stored on PACS (Picture Archiving and Communication System) under this study number only. Study data will be managed by the PI and co-investigators.

Data and Safety Monitoring Plan

The procedures administered for this research will be done in a manner that is consistent with clinical care. Therefore, an internal monitoring plan that includes the PI and all co-investigators will be implemented. Study team members will meet at least quarterly to discuss study progress including enrollment and data acquisition. Adverse events, if applicable, will be discussed at the

Title: Cardiac function and metabolism in young adults born premature

PI: [name]

Protocol version date: V7 04/23/2019

time of occurrence. In the event any unanticipated problems occur during the course of this research, they will be reported to the IRB in accordance with posted policies.

Adverse Event Reporting

Ethical Considerations:

1. This study will be conducted in compliance with current Good Clinical Practice of the International Conference on Harmonization and the ethical principles of the Declaration of Helsinki. The study will begin only after the UW Health Sciences Institutional Review Board (IRB) has granted approval.
2. The UW IRB approved consent form will state that subjects may withdraw from this study at any time without any change in the quality of their medical care or loss of benefits.

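### The plan does not require that readers who draw the PET regions and adjust the MRI borders be masked to birth group

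*Combined protocol and SAP*

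**What the plan says.** The PET-MRI Imaging section states: "Regions of interest (ROIs) will be manually drawn over the RV and left ventricle (LV"). This is done on three short-axis levels, and SUV is read from the regions. Besides mean SUV, the listed endpoints are "maximal SUV within RV and LV, and ratio of RV:LV ^{18}F -FDG uptake", for each of six images.

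The image-analysis text in the same section states that "RV and LV wall thickness and mass will be manually determined offline". RV volumes are obtained differently, by "semi-automated detection with fine manual adjustment of cardiac borders".

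The one remark on observers concerns how MRI is acquired: "Axial SSFP images will be acquired through the entire heart to minimize inter-observer and intra-observer variability".

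The direction expected is explicit in Specific Aim 1a: "To demonstrate enhanced cardiac glucose uptake in adults born premature utilizing 18F-fluorodeoxyglucose (FDG) PET-MRI".

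Under Privacy and Confidentiality, "PET/MR research images will be stored on PACS (Picture Archiving and Communication System) under this study number only". The same section adds: "Study data will be managed by the PI and co-investigators".

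Statistical Analysis and Power Calculations names two primary endpoints, both PET glucose uptake: the value at normoxic rest, and the change from normoxia to hypoxia.

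Nowhere does the protocol say who reads the images, what that person knows about the subject, or in what order scans are read. It gives no contouring rule and no second or repeat read for the PET regions.

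**The concern.** Birth group cannot be randomised and cannot be concealed from subjects. Masked reading is therefore the main protection available against expectation entering a measurement that depends on judgement. Where the edge of a region falls decides how much blood pool or neighbouring tissue is averaged in. A reader who knows the group and expects higher uptake in preterm subjects could place edges slightly differently without intending to. A shift of that kind is added to the group difference and, in the planned t test, cannot be told apart from a true effect. The plan as written permits this.

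**Working it through.** **Inputs** (Statistical Analysis and Power Calculations): control mean slope 0.0017 at normoxic rest and 0.0033 in hypoxia, each ± 0.0007 (swine pilot, assumed by the plan to apply to controls); 30% increase; 2:1 enrolment; type I error 0.05, two-sided; power 0.8; two-sample t test; 44 preterm and 22 term.

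**Step 1: reproduce the plan's figure.** The ± is not labelled. Taking it as an SD:

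- Difference = 0.30 × 0.0017 = 0.00051; standardised, 0.00051 / 0.0007 = 0.729.
- Control n = (1 + 1/2) × (1.960 + 0.842)² × (0.0007 / 0.00051)² = 22.2.
- This rounds to 22 and 44, as stated. Power at that size is 0.797 (normal approximation) or 0.785 (noncentral t).

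The agreement supports reading the ± as an SD.

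**Step 2: precision of the group comparison.** SE = 0.0007 × √(1/22 + 1/44) = 0.000183, which is 10.8% of 0.0017.

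**Step 3: false-positive rate for endpoint 1 under an assumed reading shift.** Suppose there is no true difference and reading raises preterm uptake by a fraction b of the control mean. The t statistic (64 degrees of freedom) then has noncentrality b × 0.0017 / 0.000183, and the rate is the probability of exceeding the two-sided 0.05 limits. The values of b are assumptions.

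| Assumed shift b | Shift in slope | Shift / SE | Share of planned 30% effect | False-positive rate |
|---|---|---|---|---|
| 0 | 0 | 0 | 0 | 5.0% |
| 2% | 0.000034 | 0.19 | 7% | 5.4% |
| 5% | 0.000085 | 0.47 | 17% | 7.4% |
| 10% | 0.00017 | 0.93 | 33% | 15.0% |
| 15% | 0.000255 | 1.40 | 50% | 27.9% |

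**Step 4: endpoint 2.** Let N and H be a subject's normoxic and hypoxic uptake.

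- A constant shift c cancels in an absolute change: (H + c) − (N + c) = H − N.
- A proportional shift does not: (1 + b)(H − N) exceeds H − N by b(H − N). With the pilot change 0.0033 − 0.0017 = 0.0016 and b = 5%, the excess is 0.00008.

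The documents give no SD for the change, so no false-positive rate can be attached to endpoint 2.

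**Step 5: does study-number coding already mask the reader?** The coding separates scans from hospital records and identities. Birth group is not an identity, and no sentence withholds it from a reader. The coding therefore allows masked reading but does not impose it.

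**The case against.** The strongest reply is that the plan is silent, and silence is not evidence of unmasked reading. Data and scans carry study numbers, and files linking number to identity are limited to staff who need them, for example to contact participants. A reader working from coded scans might in practice not know the group. This stands: one might infer that readers are unmasked, but the documents do not say so. They show only that masking is not required.

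Four other inferences go further than the text allows:

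- **That the people who recruit and take birth history also draw the regions.** The protocol says the investigators manage the data; it does not identify the readers.
- **That all borders are hand-drawn.** RV volumes start from semi-automated detection. The MRI measures are also not primary endpoints.
- **That the bias would be permanent.** PET data are kept in list mode and scans are stored, so a masked re-read would remain possible.
- **That both primary endpoints are necessarily biased.** Step 4 shows that a constant shift leaves an absolute change untouched.

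The size is also open to challenge. The shifts have no source in the documents. At 2% the effect is negligible, and at 5% the shift is under half a standard error. Maximal SUV depends less on edge placement than mean SUV does. The primary endpoints are not tied to the RV, where a thin wall would make placement matter most. All of this limits the claim about size. It does not supply the missing requirement.

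**Conclusion.** The point holds as an omission: a manual measurement feeds the PET uptake endpoints of a non-randomised comparison with a stated direction of expectation, and masked reading is not required.

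The consequence for endpoint 1 ranges from trivial (5.4% at an assumed 2% shift) through 7.4% at 5% to a threefold rise in the false-positive rate (15% at 10%). Endpoint 2 is exposed only to a shift that differs between normoxia and hypoxia. These figures assume that the ± is an SD, that the swine values apply to human controls as the plan assumes, that a reading shift carries through to the slope used for sizing, and that endpoint 1 is tested at two-sided 0.05. Whether any shift would occur, and how large it would be, cannot be learned from the documents. The case for change rests on the low cost of prevention, not on evidence that bias is present. The sample size is unaffected.

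**What to change.** Add to the image-analysis text of the PET-MRI Imaging section a requirement that:

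- PET regions and MRI borders are drawn by an existing team member who has no access to birth group or birth history;
- scans are presented under study codes that do not encode group;
- scans are read in random order across groups;
- readings are locked before group is linked.

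The cost is a short protocol addition, a coded reading list, and minor coordination to keep the reader away from birth data. It needs no additional subjects. It needs no additional reader either, provided someone on the team can be kept apart from birth information; the protocol does not describe staffing closely enough to confirm this. Masked repeat reads of a subset are optional: they would describe repeatability but would not detect a systematic difference between groups.

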PET-MRI Imaging: The subject will be escorted to the GE Discovery 750W 3T MR scanner containing the PET insert, located in the basement level of WIMR Tower 1, where they will undergo simultaneous cardiac PET/MR scanning. 3.7 MBq/kg (with a maximum 10 mCi dose) of ^{18}F -fluorodeoxyglucose (FDG) will be administered intravenously at a constant infusion rate of 0.01ml/s – 0.05ml/s in a large-bore indwelling catheter in the arm (preferably in an antecubital vein) by a nuclear medicine technologist. The continuous infusion will be maintained by a Medrad® Spectra Solaris syringe pump. The injection site will be inspected by the technologist to assess for any possible infiltration. Simultaneous PET/MR scanning will be conducted during ^{18}F -FDG administration.

After a period of obtaining baseline resting normoxic images (10-20 minutes of scanning time), the subject will breathe hypoxic gas (FiO_2 0.12) through a low-resistance two-way non-rebreathing mouthpiece for the remainder of the scan (total duration of scan estimated at 60-90 minutes, with a maxi of 120 minutes, and hypoxic portion estimated at 40-45 minutes, with a max of 60 minutes) to enhance glucose uptake, similar to what has previously been described by Chen and colleagues.²²

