Venous cannulation: Two intravenous (IV) lines will be placed by qualified study personnel. Blood for biobanking and monocyte studies will be collected at this time, typically during placement of one of the IV lines. Lidocaine may be administered as a local anesthetic. One IV will be used for FDG infusion, and the second used for initial laboratory draw as well as serial labs during the imaging scan. Alternatively, blood samples may be collected by finger stick or venipuncture (inserting a needle into a vein without a catheter). During the imaging scan, we will collect 0.5 – 2 ml blood every 10 minutes. Blood samples will be centrifuged to obtain plasma, and aliquot in a gamma counter calibrated to the PET scanner to measure activity during the experiment. We will also perform lactate and glucose assessment every 10 minutes during the study. The purpose of lactate measurements is to account for changes in lactate which is a measure of anaerobic metabolism during hypoxia. Entire amount of blood drawn will not exceed 80 ml.

Health questionnaires: The subjects will answers health questionnaires, a Pre-Session Questionnaire and Symptom Questionnaire.

Medical records: General information regarding birth history will be asked of all subjects (i.e. gestational age, birth weight). For adults born premature, additional birth history will be collected from Newborn Lung Project medical records or birth hospitals. This information will include prenatal characteristics (including but not limited to: maternal age, demographics, gravidity, comorbidities such as diabetes, hypertension, asthma, tobacco use, alcohol use, antenatal steroid use), birth and postnatal characteristics (including but not limited to: gestational age, anthropometric data, delivery type, and data regarding neonatal comorbidities such as bronchopulmonary dysplasia, intracardiac shunts, sepsis, respiratory failure, nutrition), and childhood characteristics (including but not limited to: anthropometric data, history of early wheezing, cigarette exposure, treatment for respiratory illnesses such as bronchopulmonary dysplasia and asthma, and serial pulmonary function testing).

Compensation:

\$100 for completion of study visit. Parking validation and travel expenses (ie mileage) will be provided for research subjects. Compensation may be prorated at \$20/hr if a subject is unable to complete the visit.

Risks:

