3. Each subject is required to sign a HIPAA Research Authorization at the time of consent. This authorization clearly outlines who will have access to specified protected health information. The information obtained in these studies is not particularly sensitive. However, data will be coded by subject identification numbers and any key linking this code number to subject identifiers will have access limited to the investigator and key study personnel all of whom have had HIPAA training required by the University of Wisconsin. Data will be stored in files and a computer database, both in a locked location with access only by study personnel. Data obtained from the study may be published in scientific journals or presented in scientific meetings, but results will be coded so individuals are not identified. Records will be retained by the Principal Investigator in compliance with UW institutional policy.

Statistical Analysis and Power Calculations:

T
The primary endpoints are (1) PET glucose uptake during normoxic rest and (2) the change in glucose uptake from normoxia to hypoxia, or substrate flexibility. Our prior pilot study (n=10) using the same PET/MRI rest-stress (hypoxia) protocol in swine demonstrated a myocardium to blood pool time activity curve slope of 0.0017 ± 0.0007 during normoxic rest, increasing to 0.0033 ± 0.0007 during hypoxia exposure. We assume similar values for control subjects and estimate at least a 30% increase in normoxic resting glucose utilization in young adults born premature. Thus, with a 2:1 enrollment strategy and an overall type I error of 0.05 and power of 0.8, we will need a study size of 44 preterm and 22 term subjects.

For the monocyte metabolism studies, oxidative stress has not previously been measured in a cohort of preterm born young adults, limiting the ability to conduct a true power analysis. However, studies of similar measures of bioenergetic health in cardiovascular disease, autism, Alzheimer's disease, and fibromyalgia have included 8-20 subjects per group.^{28,29} Since the proposed studies will be paired with PET-MRI imaging, we propose completing the mitochondrial

Title: Cardiac function and metabolism in young adults born premature

PI: [name]

Protocol version date: V7 04/23/2019

analysis on all subjects enrolled for PET-MRI imaging with an interim assessment for true power calculations.

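### The PET section measures uptake by SUV, but the sample size rests on a myocardium-to-blood slope; if SUV is used, the normoxia-to-hypoxia change is confounded with scan time

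*Combined protocol and SAP*

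**What the plan says.** All of this is in the combined protocol and SAP.

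- **Statistical Analysis and Power Calculations.** The primary endpoints are ("1) PET glucose uptake during normoxic rest and (2) the change in glucose uptake from normoxia to hypoxia, or substrate flexibility"). No PET measure is named for either. The sample size uses a swine pilot with a "myocardium to blood pool time activity curve slope of 0.0017 ± 0.0007 during normoxic rest", "increasing to 0.0033 ± 0.0007 during hypoxia exposure". Control subjects are assumed to be similar, and the authors "estimate at least a 30% increase in normoxic resting glucose utilization in young adults born premature". Rest and stress measures go into a repeated measures model with groups and exposures. No term for time or tracer supply is stated.
- **Research Procedures, PET-MRI Imaging.** FDG "will be administered intravenously at a constant infusion rate of" 0.01 to 0.05 ml/s, with scanning during administration. Normoxic images take the first 10-20 minutes and hypoxia follows for the rest of the scan. Six 10-minute images are reconstructed from list-mode data, "and standardized uptake value (SUV) determined to quantify" uptake. The listed endpoints are mean and maximal SUV in each ventricle and the RV:LV ratio, per image. Metabolic efficiency is also built on maximal SUV.
- **Venous cannulation.** Plasma from samples drawn every 10 minutes is counted in a "gamma counter calibrated to the PET scanner to measure activity during the experiment". No endpoint is said to use the result.

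Nowhere does the plan say which images make up the normoxic and hypoxic values.

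**The concern.** SUV is the tracer present in tissue at a given time, scaled to dose and body size. During a continuing infusion of a trapped tracer it climbs because more tracer has been delivered and retained. Hypoxia always follows normoxia, so a later-minus-earlier difference in SUV mixes any hypoxia effect with elapsed time. The model as described has nothing to separate the two.

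Accumulation is also faster where the uptake rate is higher. A group with higher resting uptake therefore shows a larger SUV change even if hypoxia alters nothing. The second primary endpoint, meant to capture substrate flexibility, would then partly repeat the first.

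Finally, the planning slope is not defined as a measurement in human subjects anywhere in the plan, so the power statement is not tied to a described endpoint.

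**Working it through.** **1. The plan's sample size.** Inputs from the statistics section: control slope 0.0017; SD 0.0007 (reading the ± as an SD); difference 0.30 × 0.0017 = 0.00051; 2:1 allocation; two-sided 0.05; power 0.80.

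- Term n = (1.960 + 0.842)² × SD² × (1 + 1/2) / difference² = 7.849 × 0.0007² × 1.5 / 0.00051² = 22.18. The total is 3 × 22.18 = 66.5.
- At 22 + 44: SE = 0.0007 × √(1/22 + 1/44) = 0.000183, and 0.00051 / 0.000183 = 2.79. Power is 79.7% (normal) or 78.5% (t test).

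The stated 44 + 22 reproduces, on the slope. No SUV mean or SD is given, so power on SUV cannot be computed.

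**2. SUV with no hypoxia effect.** The plan supplies the constant infusion, the order of conditions and the six 10-minute images. Images 1-2 are taken as normoxic (a 20-minute baseline). The kinetics are assumptions: free tracer E and trapped tracer M, with dE/dt = K1·B − (k2 + k3)·E and dM/dt = k3·E, and signal = 0.9(E + M) + 0.1·B. K1 = 0.3, k2 = 1.0, and k3 = 0.02, 0.05 or 0.10 per minute. Activity is decay-corrected. Blood B is either flat or 1 − exp(−ct). All constants stay the same throughout, so hypoxia does nothing. Scaling by dose and weight cancels in the ratio.

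| Blood curve | SUV, images 3-6 / images 1-2 (k3 = 0.02, 0.05, 0.10) | Myocardium-to-blood slope, 20-60 min / 10-20 min |
|---|---|---|
| Flat | 1.43, 1.86, 2.34 | 1.00 |
| c = 0.3 per min | 1.70, 2.21, 2.80 | 0.96 to 1.03 |
| c = 0.1 per min | 2.35, 2.99, 3.76 | 1.00 to 1.22 |
| c = 0.03 per min | 3.60, 4.43, 5.44 | 0.90 to 1.13 |

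Hand check for flat blood, k3 = 0.05: the net rate is 0.3 × 0.05 / 1.05 = 0.0143, so the signal slope is 0.9 × 0.0143 = 0.0129 per minute. E settles at 0.3 / 1.05 = 0.286. The intercept is 0.1 + 0.9 × (0.286 − 0.0143 / 1.05) = 0.345. The mean image times are 10 and 40 minutes, giving (0.345 + 0.516) / (0.345 + 0.129) = 1.82. The simulated 1.86 is slightly higher because free tracer takes a minute or so to fill.

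**3. Between groups.** If resting uptake is equal, both groups accumulate alike and the expected difference in change is zero. Now raise the preterm net rate by 30%, through k3, still with no hypoxia effect. The preterm SUV change divided by the term SUV change is 1.28 to 1.30 with flat blood, and between 1.10 and 1.27 across the three rising blood curves. It falls below 1.30 because part of the rise comes from blood and free tracer, which both groups share.

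**The case against.** The best reply is that SUV is never called the primary measure. That is correct. The only measure in the primary-endpoint paragraph is the slope, said to come from the same imaging protocol. The aims speak of dynamic glucose uptake, and counting plasma against the scanner suggests that a blood-referenced measure may be intended. A reader might infer that the trial will analyse SUV as primary; the documents do not say so. They leave the measure undefined, and SUV and its RV:LV ratio are the only human PET measures described.

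Other stronger readings also go too far:

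- **A spurious preterm advantage whatever the truth.** Accumulation cancels on average between groups with equal resting uptake. The group contrast is biased only when resting rates differ, which is what the plan expects. Treating change as exactly slope × time without noise would make the spurious difference significant in about 79% of trials under the 30% assumption. That is an idealisation, not a forecast.
- **A fourfold artefact.** If tissue activity were simply proportional to time, the ratio would be 40 / 10 = 4. That ignores free tracer and blood signal; with flat blood the model above gives 1.43 to 2.34.
- **Infusion speed alone shifts SUV severalfold.** The rate range is fivefold, but no infused volume or duration is given. Volume could vary to hold duration fixed, so no such figure can be derived.
- **The sample size is wrong.** It reproduces on the slope. What is missing is its link to the measurement section.

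It also stands that the RV:LV ratio, a listed endpoint, cancels much of the shared accumulation.

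**Conclusion.** The concern holds in this form: the primary PET measure is undefined, the measurement and statistics sections use different quantities, and the quantity in the measurement section cannot separate hypoxia from elapsed time.

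With no hypoxia effect, SUV rises by a factor of about 1.4 to 2.3 with flat blood activity and up to about 5 with rising, saturating blood activity (about 7 in the limiting case of a linear rise). The size depends on assumed kinetics and on taking images 1-2 as normoxic. The direction was the same in every scenario with a continuing infusion, which is what the plan describes. If the infusion instead stopped early and plasma cleared fast, the ratio could fall below 1 (0.55 to 0.87 with an assumed 12-minute infusion). The bias would then change sign rather than vanish.

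A within-subject exposure effect on SUV is therefore not interpretable. Under the plan's own 30% assumption, the group difference in change is inflated by roughly 10-30% of the term group's change. The second endpoint then partly, not wholly, repeats the first. This should be settled before any PET outcome is analysed.

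**What to change.** In both the PET-MRI Imaging and the statistics sections:

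- Define both primary endpoints on the measure used for the sample size, the myocardium-to-blood-pool time-activity slope. Endpoint 1 is the normoxic slope; endpoint 2 is the hypoxic minus the normoxic slope. State the ventricle or region and the time unit.
- State the normoxic and hypoxic analysis windows and fit the slope separately in each. Six 10-minute images give only one or two normoxic points, so reconstruct the list-mode data into shorter frames.
- Take the blood reference from the blood-pool image and check it against the plasma FDG samples already drawn.
- Keep SUV and RV:LV as secondary or descriptive, with a note that SUV change includes accumulation over time.
- Report a Patlak rate, with or without glucose scaling, as a sensitivity analysis, because the simple slope still drifts when blood activity is changing. It should not replace the primary measure without new planning figures. If blood rises linearly, the integral of blood activity divided by blood activity is t/2, so the slope against time is half the Patlak slope, and 0.0017 ± 0.0007 would not carry over.

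The cost is protocol wording and extra offline analysis, with no new data. The downside is that slopes from a 10-20 minute baseline are noisier than SUV. Some residual drift also remains: the late-to-early slope ratio was 0.90 to 1.22 in the scenarios above, and 0.6 to 1.2 over a wider set of blood curves. That is far less than the drift in SUV.
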